8.2. Secondary Endpoints

Major Bleeding: was defined as clinically evident hemorrhage associated with a hemoglobin decrease ≥ 2 g/dL that leads to a transfusion of ≥ 2 units of whole blood or packed red cells outside of the perioperative period (time from the start of the surgery or procedure and up to 12 hours after), or hemorrhage that is intracranial, retroperitoneal, or into a prosthetic joint.

Number of any reported (AE) or (SAE) during the study duration.

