12. TREATMENT OF TRIAL PARTICIPANTS

12.1. Description of Study Medication(s)

Because thrombin plays a central role in thrombogenesis, the goal of most treatment regimens is to block thrombin generation or inhibit its activity.

1- r-Hirudin binds directly with thrombin to its active & fibrinogen binding site.

2- r-hirudin does not require access to heparin binding site & can thus neutralize clot bound thrombin. Hence, down regulating thrombin generation & potentially enhancing early revascularization.

Direct thrombin inhibitors were developed to overcome the inability of the heparin/antithrombin complex to inactivate bound thrombin. In contrast to heparin and low-molecular-weight heparin, which catalyze the inactivation of thrombin and activated factor X (factor Xa) by antithrombin, direct thrombin inhibitors bind to thrombin and block its interaction with its substrates.

II- They do not bind to plasma proteins, direct thrombin inhibitors produce a more predictable anticoagulant response than heparin.

III- Unlike heparin, direct thrombin inhibitors do not interact with platelet factor 4 or high-molecular-weight multimers of von Willebrand factor. Consequently, the activity of direct thrombin inhibitors in the vicinity of a platelet-rich thrombus is not compromised.

IV- Finally, thrombin bound to fibrin or fibrin degradation products is susceptible to inactivation by direct thrombin inhibitors. Because the active site of thrombin is not involved in the interaction of the enzyme with fibrin, it remains accessible to active site-directed thrombin inhibitors. Consequently, these agents inactivate fibrin-bound thrombin without displacing the enzyme from fibrin. In contrast, bivalent thrombin inhibitors, such as Hirudin and bivalirudin, displace bound thrombin during the inhibition reaction by competing with fibrin for access to exosite 1 on thrombin.

Dose of Thrombexx®:

In DVT Prophylaxis: 15 mg twice daily, subcutaneous for 15 days

In case of renal insufficiency, the dose is titrated because r-Hirudin is excreted renally.

According to Creatinine clearance:

Creatinine clearance > 31-60 ml/min (5 mg s.c twice daily)

Creatinine clearance < 31 ml/min (1.7 mg s.c twice daily)

In case of patients who will receive spinal anesthesia; Thrombexx will be given 8-10 hours before puncture/catheter and 2-4 hours after puncture/catheter manipulation or removal, as per European Guidelines.

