17. STATISTICAL METHODOLOGY

17.1. Determination of Sample Size

Sample size: Records for 100 patients who underwent major orthopedic surgery collected from 1 site

The sample size is based on literature review for previous studies, and a sample of 168 patients will be sufficient to detect an incidence of 12.5% of DVT with an acceptable error of 5%, and a 95% confidence level

17.2. Analysis Variables:

17.2.1. Primary analysis variables:

Proportion of patients experienced new onset symptomatic thrombosis
The number of clinical PE (Pulmonary Embolism) events will be measured by spiral CT

17.2.2. Secondary analysis variables:

Number of adverse events recorded
Proportion of patients experienced major bleeding

17.2.3. Statistical Method:

Descriptive analysis:

All statistical tests used a significance level of $P=0.05$, two tailed tests were performed for all analyses used statistical testing.

Descriptive analysis for quantitative data will include count, mean with 95% CI, standard deviation, median, minimum and maximum. For qualitative categorical variables; frequency and percentage and 95% confidence interval will be applied.

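### The major-bleeding definition omits spinal/epidural hematoma, and omits fatal or re-operated bleeds outside three listed sites when the hemoglobin and two-unit criteria are not met

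*Protocol*

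**What the plan says.** The definition has the same wording in the protocol synopsis, Protocol 8.2 and SAP 4.2. It has two limbs.

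- First limb: "clinically evident hemorrhage associated with a hemoglobin decrease ≥ 2 g/dL that leads to a transfusion of ≥ 2 units" (either blood product, whole or packed cells, qualifies), with the timing restriction "outside of the perioperative period (time from the start of the surgery or procedure and up to 12 hours after" (the parenthesis closes there).
- Second limb: "or hemorrhage that is intracranial, retroperitoneal, or into a prosthetic joint". No hemoglobin fall or transfusion is required here.

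Protocol 17.2.2 and SAP 8.2.2 turn this into the analysis variable "Proportion of patients experienced major bleeding". Protocol 5.2 states the objective that the variable serves: safety judged by serious bleeding. A second safety endpoint in Protocol 8.2 is "Number of any reported (AE) or (SAE) during the study duration".

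On anesthesia, Protocol 12.1 says: "In case of patients who will receive spinal anesthesia; Thrombexx will be given 8-10 hours before puncture/catheter", and goes on to timing after puncture or after catheter manipulation or removal. Type of anesthesia is recorded (Protocol 6.2) and tabulated (SAP Table 7). The planned number is given as "Records for 100 patients who underwent major orthopedic surgery collected from 1 site".

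**The concern.** Neither limb names intraspinal or epidural bleeding, a fatal outcome, or a bleed that leads to re-operation. A hematoma in the spinal canal can do serious harm without much blood loss, so it need not reach a 2 g/dL fall or two units. A patient who dies before two units are given, from a bleed outside the three sites, also fails both limbs.

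The proportion with major bleeding is the single number that a reader will set against the thrombosis results in this uncontrolled trial. Followed exactly, the plan could report 0% major bleeding alongside a fatal or paralysing bleed.

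**Working it through.** **Inputs.** The two limbs (Protocol 8.2), the provision for spinal anesthesia (Protocol 12.1), N = 100 (Protocol 17.1), and a 95% interval for categorical variables with no method named (Protocol 17.2.3). The documents give no expected bleeding rate, so the event counts below are assumptions, and the exact (Clopper-Pearson) interval is my choice.

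**The plan's own figure.** The only calculated figure is the DVT precision sample size: 1.96² × 0.125 × 0.875 / 0.05² = 168.07, which reproduces the stated 168. It does not involve bleeding, so no sample size depends on this definition.

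**Each type of bleed against each limb.**

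| Bleed | First limb | Second limb | Counted |
|---|---|---|---|
| Any site, Hb fall ≥ 2 g/dL leading to ≥ 2 units, outside the window | met | not needed | yes |
| Fatal or re-operated; intracranial, retroperitoneal or prosthetic joint | not needed | met | yes |
| Spinal or epidural hematoma without the Hb fall and two units | not met | not met | no |
| Fatal, other site, Hb or two-unit criterion missed | not met | not met | no |
| Re-operated, other site (for example wound or soft tissue outside the joint), Hb or two-unit criterion missed | not met | not met | no |

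The gap is the last three rows.

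**The definition against the rest of the plan.**

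- The primary endpoint (Protocol 8.1) makes a symptomatic thrombosis count if it needs medical or surgical intervention, and also counts death from thrombosis. Neither surgery nor death makes a bleed count.
- Protocol 16.4 classes an event as serious if it causes death or lasting disability. A bleed can be serious in that sense and not be major under 8.2.
- SAP Table 11 carries the title of the major-bleeding proportion, but its rows are only Normal/Abnormal and type of blood product. There is no row for units, hemoglobin fall, site, re-operation or fatal outcome. As laid out, it cannot show even the present definition.

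**Size.** Each uncounted patient is 1/100 = 1 percentage point. Exact 95% limits at N = 100:

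- 0 events: lower 0; upper 1 − 0.025^(1/100) = 0.0362, or 3.6%.
- 1 event: lower 1 − 0.975^(1/100) = 0.00025, or 0.03%; the upper limit solves (1 − p)^100 + 100p(1 − p)^99 = 0.025, giving p = 0.05446, or 5.4%.
- 2 events, by the same method: 0.24% to 7.0%.

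One uncounted event therefore turns 1% (0.03 to 5.4) into 0% (0 to 3.6). Two turn 2% (0.24 to 7.0) into the same 0%.

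**The case against.** The strongest reply is that the second limb already does much of the work. The population is total knee and hip arthroplasty (Protocol 9.2), so a re-operated bleed into the new joint counts whatever the hemoglobin or transfusion. A fatal bleed at any of the three sites also counts. A reader might infer that fatal and re-operated bleeds are left out altogether; the text does not support that. This part of the reply stands and limits the point to bleeds elsewhere. It does not touch spinal or epidural hematoma, which is at none of the listed sites.

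Second, the events are not lost. AE and SAE counts are an endpoint in the same section, SAEs are sent within 24 hours (Protocol 16.4.1), SAP Table 13 itemises them, and SAP Table 20 lists death and adverse event as reasons for discontinuation. A reader might infer that such a bleed would be hidden; it would not be. But none of these counts enters the major-bleeding proportion.

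Third, the definition is a consistent choice and the analysis is descriptive. No threshold, hypothesis or sample size rests on it, and the intervals above overlap heavily. That is fair, and it keeps this from being a fatal flaw.

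Three further readings are tempting but unsupported:

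- That the protocol acknowledges spinal hematoma as a hazard. Section 12.1 gives timing and refers to European guidelines; it does not mention hematoma. Only the provision for spinal anesthesia is documented.
- That the definition was carried over from a cited trial. Protocol 4.2 says major bleeding was an endpoint in one of them, but gives no definition.
- That the stopping rules would miss such a bleed. The synopsis and Protocol 15.3 list major bleeding but also rely on investigator evaluation.

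**Conclusion.** The concern holds in a limited form. The definition leaves out intraspinal and epidural hematoma in a trial that provides for spinal anesthesia. It also leaves out fatal or re-operated bleeds outside the three listed sites when the hemoglobin and two-unit criteria are not met. The fault is one of classification within one proportion, but that proportion is the variable tied to the safety objective.

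The size is 1 percentage point per affected patient at N = 100. How many such patients to expect cannot be derived from the documents; the counts of one and two are illustrations. The main consequence is qualitative: a reported 0% could stand beside a fatal or disabling bleed that is visible only under the AE/SAE and discontinuation results. This should be changed because the change is cheap, but it does not invalidate the design.

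**What to change.** For the analysis endpoint, add three criteria to the synopsis, Protocol 8.2 and SAP 4.2: fatal bleeding, intraspinal or epidural bleeding, and bleeding leading to re-operation. None should require a hemoglobin fall or a transfusion, so they belong beside the site limb.

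In SAP Table 11, add rows for the expanded definition, each of its components, and the present definition. Keeping the present definition lets a reader see what the change contributes.

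The synopsis stopping rules and Protocol 15.3 also use the term major bleeding. Give the expanded endpoint its own label and state that it is for analysis, so that the stopping rules are left unchanged.

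The cost is an amendment to wording in three places and a few table rows. No new assessment is needed: Protocol 16.1 already asks for the diagnosis, corrective treatment and outcome of every AE. The sample size is unaffected. The downside is that the reported bleeding rate may be slightly higher.

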9. STUDY POPULATION

This is a prospective study, it is important to have a well-defined study population in place prior to the start of the study. Study populations should be defined using specific inclusion and exclusion criteria, which will be used to evaluate a potential subject's ability to participate in the study.

9.1. Recruitment strategy:

It is essential that the recruitment process take into account factors that will optimize the type and number of participants enrolled in the study while minimizing time and expense. Failure to meet target accrual goals can affect the "power" of a study, making it less successful in providing quality results.

Recruitment plan will be through explaining to patients the clinical trial objective in Alexandria University hospital; referral also will be used to increase the flow rate of recruitment.

9.2. Inclusion Criteria

Patients aged 18 years of age or older

- Body Weight >60 kg
- Patients undergoing major orthopedic operations Total knee & hip Arthroplasty
- Patients ready to sign (ICF)

Patients should discontinue any agents that affect haemostasis prior to the study medication use unless strictly indicated. These agents include medications such as: anticoagulants, thrombolytics, non-steroidal anti-inflammatory agents (including Ketorolac tromethamine), preparations containing aspirin, systemic salicylates, ticlopidine, dextran 40, clopidogrel, other anti platelet agents including glycoprotein IIb/IIIa antagonists or systemic glucocorticoids.

9.3. Exclusion Criteria

Significant bleeding injury such as solid organ laceration or intracranial bleed at discretion of attending physician

Hypersensitivity to Hirudin or prior documented allergy to its components

Pregnant or breast feeding females

Hemorrhagic stroke in preceding 3 months

Abnormal baseline coagulation characterized by an INR >1.4 , obtained at the discretion of the treating clinician

Required therapeutic anticoagulation for atrial fibrillation, prior VTE, or mechanical heart valve
Treatment with concomitant anti-platelet agent other than aspirin 326 mg or more daily
Subjects with a life expectancy less than 1 month

10. STUDY PROCEDURE:

10.1. Selection of the study population:

Subjects will be selected according to inclusion and exclusion criteria, willing to sign informed consent and able to complete the study.

Subject's informed consent had to be obtained and documented in accordance with local regulations, ICH-GCP requirements, and the ethical principles that have their origin in the principles of the Declaration of Helsinki.

Prior to obtaining informed consent, information should had been given in a language and at a level of complexity understandable to the subject in both oral and written form by the investigator or designee. Each subject should have the opportunity to discuss the trial and its alternatives with the investigator. the written Informed Consent Form should have been signed and personally dated by the subject, or his legal representative, and by the person who conducted the informed consent discussion (investigator or designee). The subject or his legal representative must had received a copy of the signed and dated Informed Consent Form. As part of the consent process, each subject must have consented to direct access to his medical records for trial-related monitoring, auditing, IRB/IEC review and regulatory inspection.

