Clinical & laboratory investigations	
For Events of Deep Vein Thrombosis (DVT) within 15 days post-op.)
 
All of the patients underwent Routine bilateral compression Doppler.
 
For Clinical PE (Pulmonary Embolism) Events from Day of surgery and During Hospitalization period or end of study
 
Clinical PE events PE (Pulmonary Embolism) events were confirmed by spiral CT.
 
For follow up:
 
APTT should be done before the first dose then after 4 & 8 hours of the first dose, then on days 1,8,15 post operatively.

Study duration	
Enrolment period: 3 months duration
 
Follow-up duration: Follow-up per patient will be for a period of 15 days

Eligibility Criteria	
Inclusion Criteria:
 
 18 years of age or older Body Weight >60 kg Patients undergoing major orthopedic operations

	
Patients ready to sign informed consent form (ICF) Patients should discontinue any agents that affect haemostasis prior to the study medication use unless strictly indicated. These agents include medications such as: anticoagulants, thrombolytics, non-steroidal anti-inflammatory agents (including Ketorolac tromethamine), preparations containing aspirin, systemic salicylates, ticlopidine, dextran 40, clopidogrel, other anti-platelet agents including glycoprotein IIb/IIIa antagonists or systemic glucocorticoids.
 
Exclusion Criteria:
 
Significant bleeding injury such as solid organ laceration or intracranial bleed at discretion of attending physician Hypersensitivity to Hirudin or prior documented Allergy to its components Pregnant or breast feeding Hemorrhagic stroke in preceding 3 months abnormal baseline coagulation characterized by an INR >1.4, obtained at the discretion of the treating clinician Required therapeutic anticoagulation for atrial fibrillation, prior VTE, or mechanical heart valve Patients with a history of coagulation disorder Treatment with concomitant anti-platelet agent other than aspirin 326 mg or more daily (Platelet count < 100 X10⁹ /dl) Active bleeding Subjects with a life expectancy less than 1 month

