12.2. Concomitant Medication (if applicable)

Throughout the study Investigators might prescribe any concomitant medications or treatments deemed necessary to provide adequate supportive care except for those listed in the exclusion criteria. If these were required, the participant will be withdrawn.

Any medication, other than the study medication had taken during the study will be recorded in the CRF.

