15.2. AMENDMENT TO THE PROTOCOL

Modifications of the signed protocol are only possible by approved protocol amendments authorized by Minapharm. The protocol amendments will be approved by the IRB/IEC prior to implementation. The Investigator must not implement any deviation from, or change to the protocol, except where it is necessary to eliminate an immediate hazard to trial subject or when the change(s) involves only logistical or administrative aspects of the trial.

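### Read literally, the antiplatelet exclusion bars lower-dose aspirin but not aspirin at 326 mg or more daily, and protocol 12.2 uses the same list to decide withdrawals

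*Protocol*

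**What the plan says.** Protocol 9.3 lists as an exclusion "Treatment with concomitant anti-platelet agent other than aspirin 326 mg or more daily". The same sentence stands in the synopsis eligibility criteria and in SAP 5.3, where it is a single numbered item (number 8). No other part of either document gives an aspirin dose.

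Two other rules bear on it:

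- **Before study drug.** An inclusion item in protocol 9.2, repeated in the synopsis and SAP 5.2, reads "Patients should discontinue any agents that affect haemostasis prior to the study medication use unless strictly indicated". Its list of agents includes "preparations containing aspirin, systemic salicylates", with no dose limit.
- **During the study.** Protocol 12.2 lets investigators prescribe "any concomitant medications or treatments deemed necessary to provide adequate supportive care except for those listed in the exclusion criteria". It then adds: "If these were required, the participant will be withdrawn".

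Major bleeding is a secondary endpoint. Its definition in protocol 8.2 covers "hemorrhage that is intracranial, retroperitoneal, or into a prosthetic joint", as well as overt bleeding with a haemoglobin fall and transfusion.

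**The concern.** An exclusion with a lower dose bound on aspirin would normally keep out the higher dose. This sentence does the opposite: the words after *other than* are the exemption, and the exemption is the higher dose. Because 12.2 borrows the exclusion list, the reversal carries over from eligibility into the rule for who stays in the trial.

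The two directions have different costs:

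- **Higher dose not excluded.** This is the safety side. Aspirin at 326 mg or more daily could be given alongside a direct thrombin inhibitor after joint replacement, in a trial that counts major bleeds. With one arm there is no control group to help separate an aspirin effect from a study-drug effect. The concomitant-medication table in the SAP (Table 21) has no dose breakdown, so it would not show the problem.
- **Lower dose excluded.** Keeping these patients out adds no bleeding risk. The cost is patients turned away or withdrawn, probably without that being intended.

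**Working it through.** No arithmetic applies, and there is no figure in the plan to reproduce. The check compares the possible readings of the sentence and then follows each through the rules it touches.

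**Step 1. What the sentence can mean.**

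| Reading | Aspirin below 326 mg daily | Aspirin 326 mg or more daily | Other antiplatelet agents | Support |
|---|---|---|---|---|
| A. Literal: the exemption is aspirin at the stated dose | excluded | not excluded | excluded | The words as they stand |
| B. The dose belongs to the non-aspirin agents | not excluded | not excluded | excluded only at 326 mg or more | One milligram limit for all other agents makes no clinical sense |
| C. Two rules run together: non-aspirin agents, or aspirin at the stated dose | not excluded | excluded | excluded | Clinically plausible, but needs words that are not in the text |

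Only reading C keeps out the higher aspirin dose, and it has to be supplied by the reader. SAP 5.3 prints the sentence as one numbered item, so a lost list break does not explain the wording.

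**Step 2. Entry.** Protocol 9.2 acts first. Aspirin that is not strictly indicated is stopped at any dose, so readings A and C give the same result for those patients. They differ only where aspirin is strictly indicated.

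**Step 3. Treatment.** Protocol 9.2 is worded for the time before study drug. Study drug starts 6 hours after surgery or once haemostasis is adequate, and runs for 15 days. In that period 12.2 is the concomitant-medication rule: a necessary drug is allowed unless it is on the exclusion list, and needing a listed drug means withdrawal.

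**Step 4. The decisions compared.**

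| Situation | Literal text (A) | Two-item wording (C) |
|---|---|---|
| Entry, aspirin not strictly indicated, any dose | stopped | stopped |
| Entry, strictly indicated, up to 325 mg daily | excluded | allowed |
| Entry, strictly indicated, 326 mg or more daily | not excluded by this item | excluded |
| On treatment, up to 325 mg daily needed | withdrawn | stays |
| On treatment, 326 mg or more daily needed | may stay | withdrawn |
| Any other antiplatelet agent | excluded or withdrawn | excluded or withdrawn |

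Four of the six rows reverse, and all four concern patients who need aspirin.

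**Step 5. Size.** Neither document gives a rate of aspirin use or of strict indication. The number of patients affected cannot be derived, and neither can any shift in the thrombosis or bleeding proportions. For scale only: with 100 planned patients, one major bleed is 1/100, or 1 percentage point of that secondary proportion.

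**The case against.** The strongest reply is that investigators will read the sentence as reading C, because the cut-off makes sense only that way, and that the fault is therefore ambiguity and not error. It is a drafting fault and not a chosen design, and the likely intent is not hard to guess. But the written words give a definite answer, the same one in three places, and reading C needs added text. Staff who apply the sensible rule would be departing from the approved criteria.

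The second reply is that 9.2 already deals with aspirin: telling patients to stop drugs that affect haemostasis before starting an anticoagulant implies staying off them. Much of this stands. It confines the entry effect to strictly indicated aspirin and arguably discourages aspirin afterwards. It does not close the gap, because 9.2 exempts strict indications and 12.2 expressly allows any necessary drug that is not on the exclusion list.

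A third reply concerns the remedy. Two-item wording would permit aspirin up to 325 mg daily with a direct thrombin inhibitor, which the literal text forbids. That is correct, and it has to be put to the sponsor openly.

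Three stronger inferences are tempting and are not supported:

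- A reader might infer that all 100 planned patients are affected because all are subject to 12.2. Being under the rule is not being changed by it; only those who need aspirin are.
- A reader might infer that the bleeding results will be distorted. Nothing in the documents shows how many patients, if any, would take 326 mg or more daily.
- A reader might infer a further fault from the platelet limit that follows the sentence in the synopsis. The exclusion items there run on without separators, so this may be layout only and is not part of the point.

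**Conclusion.** The criterion is wrong as written in all three places. It exempts aspirin at 326 mg or more daily and excludes lower doses, and 12.2 carries that result into on-study withdrawals. It should be corrected: the consequence bears on safety and the repair is small. It does not touch the primary endpoint definition, the sample size or the analysis method.

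The rule reverses at a single dose, for patients with strictly indicated aspirin at entry and for patients who need aspirin during the 15 treatment days. Their number is unknown.

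Confidence is high on the wording and its literal effect. It is lower on intent, which is an inference, and on practical harm, which may be small if few patients need aspirin or if the site already applies the likely intent. The conclusion assumes that 12.2 governs the treatment period as worded.

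**What to change.** In the synopsis, protocol 9.3 and SAP 5.3, replace the sentence with two exclusion items:

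1. Treatment with any antiplatelet agent other than aspirin.
2. Treatment with aspirin at 326 mg or more daily.

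Before adopting this, the sponsor and investigator should confirm two things: the dose limit, and that aspirin up to 325 mg daily is meant to be allowed with the study drug. If it is not, exclude aspirin at any dose. Section 12.2 then follows the corrected list and needs no edit.

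The cost is one sentence replaced in three places, with no new data or procedures. The change needs a protocol amendment, and under protocol 15.2 "The protocol amendments will be approved by the IRB/IEC prior to implementation". The downside of the two-item version is that it permits low-dose aspirin alongside a direct thrombin inhibitor, which the present wording, read literally, does not. That is a clinical decision to be made explicitly, not left to follow from a wording correction.
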